3.8 Sample Size

The primary objective of the proposed study is a composite of unplanned cardiovascular hospitalizations in AF patients and any AF-related emergency department visits. The sample size calculation is based on the test of the null hypothesis that the percentages of patients with cardiovascular hospitalizations in the two populations (CDSS and usual care) are equal. The primary measure of effect is the difference in proportions of patients with composite of any AF-related emergency department visit or unplanned CV hospitalization over 12 months. The criterion for significance (alpha) has been set at 0.05. With the proposed sample size of 1075 primary care patients (537 per intervention/control arm, assuming a 1:1 allocation ratio), the study will have power of 80% to yield a statistically significant absolute difference of 10% (or 20 [RRR] relative risk reduction) between the two percentages of patients with composite of any AF-related emergency department visit or unplanned CV hospitalization in the control and intervention groups, assuming 50% annual rate of CVD hospitalizations for the control group. This sample size was adjusted for a potential clustering of patient outcomes within a physician, by assuming an intra-physician correlation coefficient (ICC) of 0.05 with an average cluster size of 9 patients/physician. The ICC is based on studies done in the primary care sector reporting this magnitude of ICC. This extent of reduction was felt to represent a minimal clinically important achievement by a consensus of study investigators and has been an endpoint target in other studies in AF populations of similar design [127-129].

Table 3 provides a summary of the sample size calculation for different values of the baseline control rate (50%, 58%), RRR (15%, 20%, 25%, 30%), intra-class correlation coefficient [ICC] (0.05, 0.10) and average cluster size (m) (9,12,15). The primary measure of effect is the difference in the proportions or percentages of patients with cardiovascular hospitalizations and AF-related emergency room visits across study arms over an active study period of 12 months. The criterion for significance (alpha) has been set at 0.05. The test is 2-tailed, which means that an effect in either direction will be interpreted. The statistical power is set at 80%.

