The analysis and reporting of the trial results will follow the CONSORT Statement for cluster-randomization trials [129]. The baseline characteristics of the practices and patients will be reported by group as mean (standard deviation) or median (first quartile, third quartile) for continuous variables, depending on the distribution, and count (percent) for categorical variables. The analysis will follow the intention-to-treat (ITT) principle. The unit of randomization will be the practice. The unit of analysis will be the patient. We will use multiple imputation to handle missing data to enable ITT analysis. Multiple imputation is a Monte Carlo technique in which the missing values are replaced by $m > 1$ simulated versions, where 'm' is typically small. Each of the simulated complete datasets will be analyzed by standard methods, and the results will be combined to produce estimates and confidence intervals that incorporate missing data uncertainty [133]. We will use generalized estimating equations (GEE) – assuming exchangeable correlation structure for patients within the same practice, and adjusting for urban and rural practice types to analyse all outcomes [130]. Unlike ordinary regression techniques, GEE allows us to model the intra-practice correlation among patients within each practice. The results will be reported as the estimate of the effect, corresponding 95% confidence interval and associated p-values. All p-values will be reported to three decimal places with those less than 0.001 reported as $p < 0.001$. The criterion for statistical significance will be set a priori at $\alpha = 0.05$, and adjusted using the Bonferroni method for multiple secondary analyses. All analyses will be performed using SAS 9.4 (Cary, NC).

Sensitivity analyses: 1) There are several methods for analyzing cluster RCTs [131]. Therefore, we will perform sensitivity analyses using some of the commonly used patient-level methods such as random-intercept model and cluster-level (i.e. random- and fixed-effects meta-analytic) methods to assess the robustness of the results. 2) Given that the unit of randomization is the practice, there is a higher chance of potential imbalance of patient-level baseline characteristics. We will perform some sensitivity analysis to adjust for any potential imbalance.

HRQoL

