We have developed a CDSS tool that aims to empower improvement in overall AF-related care, not simply with regards to antithrombotic management, but also to support effective rate control and treatment of AF risk factors. The tool has been assessed in a preliminary fashion by a general cardiologist, electrophysiologist and primary care physician, working independently to assess the

utility and dependability of the CDSS using mock clinical cases. While it functioned accurately and with seeming efficacy, there remains the need to determine applicability, ease of use and clinical effectiveness in terms of whether AF patient care and outcomes would improve at the population level with its use.

The primary aim of Integrated Management Program Advancing Community Treatment of Atrial Fibrillation (IMPACT-AF) study is to evaluate whether a CDSS tool, available to primary care physicians, and designed to support both practitioners and patients with evidence-based AF management, can improve clinical and patient-reported outcomes by comparison to usual clinical care. It further seeks to establish whether it will better standardize process of care so as to produce more efficient and cost-effective use of time and scarce health care resources as compared to usual care.

Methods

IMPACT-AF is a prospective, randomized, un-blinded, cluster design clinical trial, conducted in the primary care setting of Nova Scotia, Canada.

At least 200 primary care providers are being recruited and randomized at the level of the practice to control (usual care) or intervention (eligible to access to CDSS) cohorts. Over 1,000 patients of participating providers with confirmed AF will be managed per their provider's respective assignment.

Outcomes

Primary Outcome

The IMPACT-AF primary outcome is composite of any AF-related emergency department visit or unplanned CV hospitalization over 12 months.

Secondary Outcomes

Secondary outcomes include comparing the intervention versus usual care over 12 months on the following:

- 1. Any AF-related emergency department visit
- 2. Unplanned cardiovascular (CV) hospitalization
- 3. Strokes
- 4. Systemic embolism / major bleeding
- 5. Mortality
- 6. Anticoagulant therapy
- 7. Access to specialist consultation

- 8. Echo
- 9. Catheter ablations
- 10. EQ5D
- 11. Health care costs

The definitions of all outcome variables for the primary and secondary analyses are found in Appendix 1.

Analysis Plan

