This statistical analysis plan follows the JAMA Guidelines for the Content of Statistical Analysis Plans in Clinical Trials ¹³. A summary of all planned analyses is provided in **Table 1**.

Blinded Analyses

All statistical analyses will first be completed using blinded treatment groups (i.e. treatment X and Y).

Presentation of Data

The trial results will be presented according to the CONSORT guidelines for randomized controlled trials (RCTs) 14 . The baseline demographic characteristics of the patients will be summarized by group, reported as a mean (standard deviation [SD]) or median (first quartile, third quartile) for continuous variables and count (percent) for categorical variables (**Tables 2**). All statistical tests will be 2-tailed with α =0.05.

Primary Outcome Analysis

The primary efficacy analysis will be an analysis to compare rates of the composite of any AF-related emergency department visit or unplanned CV hospitalization between Intervention and Usual care over 12 months, with the outcome being treated as number of events (Tables 3). The analysis will follow the intention-to-treat (ITT) principle. While the unit of randomization is the practice/physician, the unit of analysis will be the patient. We will use Generalized Estimating Equations (GEE) —assuming exchangeable correlation structure for patients within the same practice and adjusting for urban and rural practice types to analyze all outcomes¹⁵. Unlike ordinary regression techniques, GEE allows us to estimate the intra-practice correlation among patients within each practice. For time-to-event analysis this is done using frailty-models. The results will be reported as estimate of the effect—reported as hazard ratio [HR], corresponding 95% confidence interval and associated p-values. All p-values will be reported to three decimal places with those less than 0.001 reported as p<0.001. The criterion for statistical significance will be set a priori at alpha = 0.05. The answers to the five questions in the EQ-5D-5L will be converted to health utilities using the Canadian scoring algorithm¹⁶. Cost effectiveness analysis

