will be conducted by calculating the incremental cost per QALY gained by the CDSS arm compared with the usual care arm. Due to skewness of costs and health utility distributions, the non-parametric bootstrapping method will be used to estimate the 95% confidence interval for the incremental cost per QALY gained. All analyses will be performed using SAS version 9.4 (Cary, NC).

Secondary Outcomes Analysis

We will estimate the effect of CDSS (intervention) versus usual care (control) over 12 months on the following: any AF-related emergency department visit; unplanned CV hospitalization; strokes; systemic embolism / major bleeding; mortality; anticoagulant therapy; access to specialist consultation; echo; catheter ablations; EQ5D; health care costs (Table 3). The subgroup analyses will be performed by adding an interaction term of the subgroup variable and the intervention variable in the model. The criterion for statistical significance for subgroup analyses will be set at alpha = 0.05. This will not be adjusted for multiple testing as these analyses are exploratory.

Sensitivity Analyses

There are several methods for analyzing cluster RCTs^{17, 18}. We will conduct sensitivity analyses in two ways. Firstly, we will perform sensitivity analyses using commonly used patient-level methods such as random-intercept model method (Table 4a). Secondly, we will also perform sensitivity analyses with the outcome (composite of any AF-related emergency department visit or unplanned CV hospitalization) being treated as a count assuming a Poisson distribution (Table 2). The results will be reported as incidence rate ratio [IRR], 95% CI and associated p-value. We hypothesize that our results will remain robust to the different sensitivity analyses.

Subgroup Analyses

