1) Primary To compare rates of the composite of any AF-related emergency department visit or unplanned CV hospitalization between Intervention and Usual care over 12 months	composite of any AF-related emergency department visit or unplanned CV hospitalization over 12 months	Intervention better than Usual Care	Generalized Estimating Equations (GEE) or frailty models
2) Secondary To compare I vs UC over 12 months on the following: any AF-related emergency department visit	any AF-related emergency department visit	Intervention better than Usual Care	GEE or frailty models
unplanned CV hospitalization	unplanned CV hospitalization	Intervention better than Usual Care	GEE or frailty models
strokes	strokes	Intervention better than Usual Care	GEE or frailty models
systemic embolism / major bleeding	systemic embolism / major bleeding	Intervention better than Usual Care	GEE or frailty models
mortality	mortality	Intervention better than Usual Care	GEE or frailty models
anticoagulant therapy	anticoagulant therapy	Intervention better than Usual Care	GEE or frailty models
access to specialist consultation	access to specialist consultation	Intervention better than Usual Care	GEE or frailty models
echo	echo	Intervention better than Usual Care	GEE or frailty models

catheter ablations	catheter ablations	Intervention better than	GEE or	frailty models
		Usual Care		
EQ5D	EQ5D	Intervention better than	GEE or	frailty models
		Usual Care		
health care costs	health care costs	Intervention better than	GEE or	frailty models
		Usual Care		
3) Subgroup Analyses:				
To compare the effect of I				
vs UC by different	All primary and	Effects on outcomes	Regres	sion methods with
subgroups: location of	secondary outcomes	differ by location of	approp	riate interaction
practice, patient sex,		practice	term	
age, CHADS2, CHADS-				
VASC, hypertension,				
diabetes and years of				
practice of family doctor				
4) Sensitivity Analyses:	composite of any	Results will remain	i)	patient-level
i) To assess the robustness	AF-related	robust		methods such as
of the results to different	emergency			random-intercept
methods of adjusting for	department visit or			model and
clustering;	unplanned CV			cluster-level [i.e.
ii) To assess the robust	hospitalization			random- and
ness of the results if the				fixed-effects
outcome is treated as the				meta-analytic]
count (number of events)			ii)	GEE using
				Poisson
				distribution

IMPORTANT REMARKS:

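### The protocol promises a Bonferroni adjustment for the secondary analyses; the SAP repeats the 0.05 criterion without it and so, read as written, tests 11 secondary outcomes unadjusted

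*Protocol*

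**What the plan says.** **Protocol.** Section 3.9 fixes significance in advance at 0.05 and then has it "adjusted using the Bonferroni method for multiple secondary analyses". It names no family size, no adjusted level and no list of the analyses that count. Section 2.2 gives the secondary outcomes under clinical, process-of-care, quality-of-life, cost and cost-effectiveness headings. It keeps major bleeding apart as the primary safety outcome.

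**SAP.** Four places bear on the point.

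- Under Presentation of Data: "All statistical tests will be 2-tailed with" alpha 0.05.
- Under Primary Outcome Analysis: "The criterion for statistical significance will be set a priori at alpha = 0.05". The sentence ends there, without the protocol's Bonferroni clause.
- The Secondary Outcomes list is numbered to "11. Health care costs". Table 1 gives each item the hypothesis "Intervention better than Usual Care".
- Under Secondary Outcomes Analysis: "We will estimate the effect of CDSS (intervention) versus usual care (control) over 12 months on the following". No significance level is stated for these outcomes. The paragraph then turns to subgroups, sets them at 0.05 and adds: "This will not be adjusted for multiple testing as these analyses are exploratory".

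The SAP mentions neither Bonferroni nor any other procedure for the secondary outcomes, and it does not say that it departs from the protocol.

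**The concern.** The two documents can give different answers from the same secondary p-value. The outcomes at stake include stroke, mortality, quality of life and health care costs, and the trial's stated purpose covers efficiency as well as clinical outcome. None of the 11 is labelled exploratory, each carries a directional hypothesis, and SAP Table 3 provides p-value columns for the secondary rows that it shows. A positive secondary result could therefore be reported as confirmatory under the SAP when the protocol's rule would not allow it. With both rules on paper, the choice between them could be made once the p-values are known.

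**Working it through.** **The plan's own figure.** Neither document states an adjusted level, so there is none to reproduce. The sample size is used for the power step below, so it is checked first. Inputs from Protocol 3.8: two-sided alpha 0.05, power 80%, 50% v 40%, ICC 0.05, cluster size 9.

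- Unadjusted total: 2 × (1.96 + 0.84)² × (0.5×0.5 + 0.4×0.6) / 0.1² = 768.32
- Variance inflation: 1 + (9 − 1) × 0.05 = 1.4
- Adjusted total: 768.32 × 1.4 = 1075.65, which matches the stated 1075.

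**How many outcomes.** The SAP list has 11. Protocol 2.2 has 11 bullets: clinical 4, process of care 3, quality of life 1, costs 2, cost-effectiveness 1. Leaving out the three cost and cost-effectiveness items gives 8. Counting the individual hospitalization elements as six causes instead of one bullet gives 11 − 1 + 6 = 16. So 8 to 16 is a fair range for a family that the protocol does not define.

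**Threshold and error rate.** The Bonferroni level is 0.05/k. The unadjusted chance of at least one false positive among k independent true nulls is 1 − 0.95^k.

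| k | 0.05/k | 1 − 0.95^k |
|---|---|---|
| 8 | 0.0063 | 34% |
| 11 | 0.0045 | 43% |
| 16 | 0.0031 | 56% |

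With k = 11 and Bonferroni, the error rate under independence is 1 − (1 − 0.05/11)^11 = 4.9%.

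Independence does not hold here. AF-related ED visits and unplanned CV hospitalization are the two components of the primary outcome, and stroke is one of the qualifying causes of a CV hospitalization. Overlap of this kind pulls the 43% down; the documents give no correlations from which to say how far.

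**Where the documents disagree.** At k = 11 they differ only for p-values above 0.0045 and up to 0.05.

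**Power cost of the protocol rule.** Take a secondary outcome with the primary's assumed rates. The effective number per arm is 537.5/1.4 = 383.9. The standard error is √(2×0.45×0.55/383.9) = 0.0359 under the null and √(0.49/383.9) = 0.0357 under the alternative.

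- At 0.05 (z = 1.96): Φ[(0.1 − 1.96×0.0359)/0.0357] = about 80%
- At 0.0045 (z = 2.84): Φ[(0.1 − 2.84×0.0359)/0.0357] = about 48%

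**The case against.** The best defence is that the SAP is silent rather than contrary. Its paragraph on secondary outcomes speaks of estimating effects and gives no alpha. The general 0.05 stands under Presentation of Data, and the criterion sentence stands under the primary analysis. The protocol also starts from 0.05 before adjusting it, so a general 0.05 could be the overall level, with the protocol's adjustment still in force. Waiving adjustment for subgroups alone could even imply that it was not waived elsewhere.

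Part of this stands: the SAP never says of the secondary outcomes, in so many words, that they are unadjusted. But a sentence that covers all statistical tests includes the secondary ones. And even on the silence reading, an analyst working from the SAP has no family, no adjusted level and no procedure to apply, so the SAP needs the same edit.

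Four stronger readings are tempting, and the documents do not support them.

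- *The SAP waives adjustment for the secondary outcomes.* The waiver sentence is about subgroup analyses only.
- *The control was removed after results were seen.* The SAP is dated January 9, 2019, after the proposed 2014–2018 period, and its baseline table shell already carries a usual-care count of 543. That shows enrolment was known, not outcomes by arm. The SAP is Version 1 and plans to complete its analyses first with blinded group labels. What can be seen is an unexplained omission.
- *0.0045 is the protocol's threshold.* It is the Bonferroni level for the SAP's list; the protocol gives no count.
- *The real false-positive risk is 43%.* That figure needs 11 independent true nulls.

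**Conclusion.** The concern holds as an unreconciled departure. The protocol commits to a Bonferroni adjustment for the secondary analyses; the SAP, read as written, tests them at two-tailed 0.05 and gives no reason.

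Its size depends on a family that the protocol leaves undefined: a threshold of 0.0045 if it is the SAP's 11 outcomes, and 0.0063 to 0.0031 for 8 to 16. Conclusions differ only for secondary p-values between that threshold and 0.05. The 43% is an illustration under independence, and the true figure is lower.

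A reader might infer that the trial's main result is at risk. It is not: Protocol 3.8 says "The criterion for significance (alpha) has been set at 0.05" for the primary comparison, two-tailed, and the SAP uses the same level. The point should be settled before secondary results are claimed, but it does not touch the primary analysis.

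**What to change.** Change the SAP as follows.

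1. Keep the statement that all tests are two-tailed. It is the SAP's only statement on sidedness, and the secondary hypotheses are worded in one direction.
2. Keep 0.05 for the primary outcome.
3. Name the secondary efficacy family and test it at overall 0.05, by Bonferroni as in the protocol or by Holm, which controls the same error and is never less powerful.
4. Keep major bleeding outside the family, as the protocol's primary safety outcome. Report it separately from systemic embolism, with which the SAP now pairs it, and without a multiplicity penalty; otherwise a signal of harm would be harder to declare. If systemic embolism stays as item 4 and nothing else changes, the family is still 11.
5. State whether the individual hospitalization elements, a secondary outcome in Protocol 2.2 and component rows in SAP Table 3, are in the family or are descriptive with confidence intervals only.
6. Record any departure from the protocol, with the reason. This applies to Holm in place of Bonferroni, to leaving listed outcomes out of the family, or to a decision to treat the secondary outcomes as unadjusted and exploratory.

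The cost is a few sentences and fewer secondary outcomes that can be called significant. Under Bonferroni with 11 outcomes, one with the primary's assumed rates falls from about 80% to about 48% power. Holm can recover some of that when other outcomes in the family are significant.

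### Where the protocol's Bonferroni adjustment of the secondary outcomes is kept, Holm's step-down method would give the same family-wise error control with slightly more power at almost no cost

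*Protocol*

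**What the plan says.** Protocol section 3.9 (Statistical Analysis) sets the significance criterion at 0.05, "adjusted using the Bonferroni method for multiple secondary analyses". It mentions no step-down variant, so the ordinary reading is the single-step rule: every secondary test is held to alpha divided by the number of tests. Section 3.9 gives neither that number nor a list of the tests. It plans a 95% confidence interval with each estimate and does not say that the intervals are adjusted.

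The SAP (Version 1, January 2019) introduces its list with "Secondary outcomes include comparing the intervention versus usual care over 12 months on the following" and numbers 11 items. It does not mention Bonferroni. Its Presentation of Data section puts all tests at two-tailed 0.05. Its only statement about multiple testing, under Secondary Outcomes Analysis, waives adjustment for the subgroup analyses.

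The protocol's own list in section 2.2 differs from the SAP's. For example, it counts the individual hospitalization elements and any bleeding as secondary, and it names major bleeding as the primary safety outcome. The SAP pairs major bleeding with systemic embolism as one secondary item.

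**The concern.** Single-step Bonferroni keeps the strictest threshold for every outcome, even after other outcomes in the family have been declared significant. Holm's method relaxes the threshold after each rejection and still holds the family-wise error at the same level. If an adjustment is to be made, the protocol's choice therefore gives up some power without buying tighter control of false positives.

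What is at stake is a modest chance of missing true effects on secondary outcomes such as the two limbs of the composite, process of care, EQ-5D and costs. SAP Table 1 hypothesises that the intervention is better on every listed secondary outcome. Several real effects at once is the setting in which a step-down rule helps most.

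**Working it through.** **The plan's own figure, and what it depends on.** Protocol section 3.8 states: "The criterion for significance (alpha) has been set at 0.05" and "The test is 2-tailed, which means that an effect in either direction will be interpreted". It sizes the trial for the composite, "assuming 50% annual rate of CVD hospitalizations for the control group", a 10-point reduction, 80% power, and an "intra-physician correlation coefficient (ICC) of 0.05 with an average cluster size of 9 patients/physician".

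- Unadjusted total: 2 × (1.96 + 0.84)² × (0.50×0.50 + 0.40×0.60) / 0.10² = 2 × 7.84 × 0.49 / 0.01 = 768.32.
- Variance inflation: 1 + (9 − 1) × 0.05 = 1.4.
- Adjusted total: 768.32 × 1.4 = 1075.65, which matches the stated 1075 and the Table 3 row.

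The alpha here is the full 0.05 for one outcome. The secondary multiplicity rule does not enter, and the documents state no power for any secondary outcome.

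**Thresholds.** Neither document fixes the family size. I assume k = 11, the SAP list.

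- Bonferroni: 0.05/11 = 0.00455 for every test. For comparison, 10 tests give 0.0050 and 20 tests give 0.0025.
- Holm, smallest p-value first: 0.05/11, 0.05/10, 0.05/9, …, 0.05/1 = 0.00455, 0.00500, 0.00556, …, 0.05, stopping at the first failure.

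**Holm rejects everything Bonferroni rejects.** If the i-th smallest p-value is at most 0.05/k, so are all smaller ones. Each Holm threshold 0.05/(k − j + 1) is at least 0.05/k, so Holm reaches that test and rejects it. The converse fails. With illustrative p-values of 0.0040 and 0.0048 and nine large ones, Bonferroni rejects one and Holm rejects two.

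**Same error control.** Suppose k₀ of the k null hypotheses are true. The first true null that Holm could reject is met no later than step k − k₀ + 1, where the threshold is at most 0.05/k₀. By the Bonferroni inequality the chance of any false rejection is then at most k₀ × 0.05/k₀ = 0.05, whatever the dependence.

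**Power per affected outcome under Bonferroni.** For a two-sided z-test with 80% unadjusted power the mean is 1.960 + 0.842 = 2.802. The critical value at 0.05/11 is 2.838. Power = Φ(2.802 − 2.838) = Φ(−0.036) = 48.6%. At 50% unadjusted power it is Φ(1.960 − 2.838) = 19.0%.

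**Power per affected outcome under Holm.** Simulation of 11 independent two-sided z-tests, 200,000 replicates per row, 80% unadjusted power for each affected outcome:

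| Truly affected, of 11 | Bonferroni | Holm | Gain (points) |
|---|---|---|---|
| 1 | 48.61% | 48.68% | 0.1 |
| 3 | 48.52% | 49.83% | 1.3 |
| 5 | 48.55% | 51.31% | 2.8 |
| 8 | 48.49% | 54.20% | 5.7 |
| 11 | 48.57% | 59.39% | 10.8 |

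The small variation in the Bonferroni column is simulation error. With a correlation of 0.3 between outcomes the gains are nearly the same. Simulated family-wise error stayed below 5% for both methods, and Holm never rejected fewer hypotheses.

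**Sensitivity to the assumed power.** At 90% unadjusted power with all 11 affected, power goes from 65.7% to 80.4%. At 50% the gain is about 0 points with one affected outcome, 1.3 with eight and 2.0 with all eleven. With a correlation of 0.3 it reaches at most 3.6.

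**The case against.** **Bonferroni is valid, pre-specified and conservative.** This stands. A reader might infer that the protocol contains a statistical error. It does not, and neither the primary test nor the sample size is touched.

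**The gain is usually small.** This also stands. A reader might infer that real effects will be lost wholesale, or that a gain of 11 to 15 points is to be expected. Those gains need all 11 outcomes to be truly affected and each to have 80 to 90% unadjusted power. The hypotheses in SAP Table 1 all favour the intervention, but they say nothing about power. The list includes stroke, mortality and catheter ablation, for which the documents give no power figure. Most of the fall from 80% to about 49% comes from correcting for 11 tests at all, and Holm recovers little of it unless most outcomes are affected.

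**The Bonferroni loss may never occur.** If the SAP alone governs, its wording allows every secondary test at 0.05, and introducing Holm would then lower power against the written plan. This limits the point to the case in which the protocol's adjustment is kept. Dropping the adjustment has its own price: 11 independent tests at 0.05 have a family-wise error of 1 − 0.95¹¹ = 43.1%.

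**Bonferroni has simple simultaneous confidence intervals that match its tests, and Holm does not.** This is true, so the power given up under Bonferroni is not wholly without return. It carries little weight here, because the plan reports 95% intervals with no stated adjustment and so does not use that advantage.

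**Conclusion.** A low-cost improvement in efficiency, not a defect. Holm dominates single-step Bonferroni on power at equal family-wise error control, and that holds without assumptions about effects or dependence.

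The size of the gain does depend on assumptions: a family of 11, and a common unadjusted power for every affected outcome. At 80% it runs from under 0.1 point with one affected outcome to about 11 points with all eleven, and is about 1 to 3 points with three to five. At 50% it is at most about 2 points with independent tests. The documents do not support choosing one value within this range, nor the reading that the plan's secondary conclusions are unsound.

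**What to change.** The protocol and the SAP have to be reconciled on whether the secondary outcomes are adjusted. If the adjustment is kept:

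1. List in both documents exactly which secondary tests form the family, and say whether the safety outcomes and costs belong to it. The gains above apply to all 11 SAP items. A smaller family would need its own calculation.
2. In protocol section 3.9, replace the Bonferroni method with the Holm step-down method (family-wise alpha 0.05, two-sided) applied to that list. Add the same sentence to the SAP's Secondary Outcomes Analysis, which has no adjustment wording now.
3. Report Holm-adjusted p-values, and label the 95% confidence intervals as unadjusted.

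The cost is a few sentences and a list. It needs no patients, no further data, and no change to the models, the primary analysis or the sample size. The one thing given up is a simple set of simultaneous intervals matching the tests, which the plan does not use.
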